Safety and Efficacy of Dexamethasone Ophthalmic Insert (Dextenza®) in the Management of
Clinically Significant Dry Eye

NCT04498468

Date: September 21, 2020

Safety and Efficacy of Dextenza in Dry Eye (V3)

Clinical Study Protocol

Safety and Efficacy of Dexamethasone Ophthalmic Insert (Dextenza®) in the Management of Clinically Significant Dry Eye

Compound:	Sustained Release Dexamethasone, 0.4 mg.
Study Name:	Safety and Efficacy of Dexamethasone Ophthalmic Insert (Dextenza®) in the Management of Clinically Significant Dry Eye.
Clinical Phase:	Phase IV, prospective, masked trial.
Date of Issue:	September 21, 2020
Principal Investigator:	[name].
Sub Investigators:	[name]. [name], OD.
Site Name & Location:	Ocular Surface Diseases and Dry Eye Clinic, The Wilmer Eye Institute, The Johns Hopkins University School Of Medicine, Baltimore, Maryland.

CLINICAL STUDY PROTOCOL SYNOPSIS

TITLE	Safety and Efficacy of Dexamethasone Ophthalmic Insert (Dextenza®) in the Management of Clinically Significant Dry Eye.
SITE LOCATION(S)	Ocular Surface Diseases and Dry Eye Clinic, The Wilmer Eye Institute, The Johns Hopkins University School Of Medicine, Baltimore, Maryland.
PRINCIPAL INVESTIGATOR	[name].
OBJECTIVE(S)	To determine efficacy and safety profile of dexamethasone 0.4mg lacrimal insert in dry eye related ocular surface inflammation.
STUDY DESIGN	Prospective, double-masked, interventional clinical trial.
STUDY DURATION	42 Days per patient, There will be 5 visits (run in, Day 1, 14, 28, and 42) with 12 months of active enrollment. Start-up period (finalizing the protocol and case report forms, obtaining approvals from institutional review board, etc): 3 months. Enrollment period: 12 months. Close-out (data completion and lock, statistical analyses, and multiple manuscript preparations etc): 3 months. Interim data analysis at 6 months. Total of 18 months
ESTIMATED STUDY COMPLETION DATE	December 31, 2021
POPULATION	Adult patients with significant dry eye or keratoconjunctivitis sicca, requiring topical steroid treatment.
Sample Size:	85 patients [1 treatment eye/1 control eye = 170 eyes] will be enrolled at a single site.
Treatment(s)	

Study Drug	Sustained release dexamethasone, 0.4 mg
DOSE/ROUTE/SCHEDULE:	Each patient's right eye will be randomized to receive either the treatment or the control. The left eye will automatically receive the alternative. For example if the right eye of the patient gets randomized to receive the study medication, left eye will automatically be the control eye. If the right eye gets randomized to receive the control treatment, the left eye will receive the study medication.
	Control eye will receive a sham treatment: commercially available tear duct plug without the dexamethasone (Vera90TM EXTENDED WEAR SYNTHETIC ABSORBABLE PUNCTAL PLUG made of E-Caprolactone-L-Lactide copolymer (PCL). Absorbs in 60 to 180 days. Size 0.5mm which is comparable to the study treatment)
	RESCUE MEDICINE: In patients with worsening of signs or symptoms, topical loteprednol 0.5% (Lotemax) drops up to 4 times a day, mimicking the usual practice, can be used at the discretion of the principle investigator.
	In patients with increased intraocular pressure (more than 5 points greater than baseline or more than 5 points higher than the fellow eye) treatment with topical beta blocker/betaxolol 0.5% (Betoptic) drops can be used 2 times a day to bring down the pressure at the discretion of the principle investigator.

Endpoint(s)

PRIMARY EFFICACY: Efficacy will be measured at 28 days.)

We have two co-primary end points:

- 1- Dry eye Sign: Corneal staining score measured using OSS scale on Day 28. The difference between the average corneal staining in the treated arm versus the average corneal staining in the sham arm will be compared statistically.
- 2- Patient reported symptom: Most bothersome symptom (any one of the (1)eye dryness, (2)eye discomfort, or (3)eye fatigue will be established as the most bothersome symptom at baseline for each eye) measured using visual analogue scale (0 to 100). The difference between the average most bothersome symptom in the treated arm versus the average most bothersome symptom in the sham arm will be compared statistically.

Secondary Efficacy:

We have two secondary end points:

- 1- Corneal staining responder analysis. Responder is defined as one full severity grade improvement in corneal staining. The percentage of subjects achieving 1 severity grade improvement in corneal staining (responders) in the treated arm versus sham arm will be compared statistically.

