1.2.1 Rationale for Study Design

We determined the sample size using STATA Statistical Software (STATA Release 12.1; STATA Corp., College Station, TX). Standard deviations from previously published data sets were used for calculations (8).

Efficacy There will be two primary efficacy measures performed at day 28. The improvement in corneal staining score (using the OSS scale) and improvement in the most bothersome symptom (using the VAS scale between 0 to 100).

Efficacy Endpoint 1: Improvement in the corneal staining score measured using OSS scoring system (0-6). With a power of 80% and significance level of 0.05, 23 persons in each group (having both eyes eligible) need to be enrolled to detect a clinically significant 3 point difference in the mean corneal staining between the treated arm versus the sham arm at day 28.

Efficacy Endpoint 2: Improvement in most bothersome dry eye symptom as measured using VAS (0 to 100). With power of 80% and significance level of 0.05, 85 persons in each group (having both eyes eligible) need to be enrolled to detect a clinically meaningful 30 point difference in the most bothersome dry eye symptom Assuming that there will be a clinically significant 30% difference in the mean most bothersome symptom between the treated arm versus the sham arm at day 28.

One problematic issue in the field of dry eye is the lack of widely agreed upon core outcomes (9). It is currently not well known for example whether improving corneal staining is clinically meaningful and how much improvement would be necessary to make a difference in what the patient is experiencing. Our previous investigator initiated studies demonstrated that corneal fluorescein staining directly relates to impairment of visual function, and reduction in reading speed (10). The relationship is linear and for each 1 severity grade increase in corneal staining (0-6), we found an average of two words per minute reduction in reading speed, using iRest out loud testing and 10 words per minute reduction in reading speed using the sustained silent reading test. Therefore, perhaps corneal staining can be used as a clinically meaningful core outcome.

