5. STUDY SCHEDULE OF EVENTS AND VISIT DESCRIPTIONS

5.1 Schedule of Events

Study assessments and procedures are presented by visit in Table 1

Table 1 Schedule of Events

Procedure	Run In* (Day -14 to -7)	Visit 1* (Day 1)	Visit 2 (Day 14)	Visit 3 (Day 28)	Visit 4 (Day 42)	Early Termination
Informed Consent	X	X**				
Inclusion/Exclusion/Demographics	X	X**				
Medical history and concurrent illnesses	X	X**				
Concomitant medications	X	X	X	X	X	X
Pregnancy Test		X			X	X
Log/Dispense Rescue Meds	X	X	X	X	X	
Insert Study Drug/Control		X				
BSCVA		X			X	X
VAS	X	X		X	X	X
Schirmer (W/O anesthesia)	X	X			X	X
OSS (corneal and conjunctival)	X	X	X	X	X	X
IOP	X	X	X	X	X	X
SLE	X	X	X	X	X	X
Dilated Fundus Exam	X	X**			X	X
Rescue med recording	X		X	X	X	X
AE recording		X	X	X	X	X

*If no run-in required, patient will start at baseline visit/ Day 1

**Required in absence of run-in visit

After having obtained an informed consent patients will be assigned a unique patient number and undergo the below procedures in the order they are listed.

1. Medical History and Review of Systems
 - i. Contact lens and glasses wearing (contact lens wear has to be discontinued 1 week prior and for the duration of the study)
 - ii. Current eye drops used:
 - a. Patients who are on dry eye drops, such as artificial tears, cyclosporine, or lifitigrast treatment will be eligible as long as the doses have been stable for at least 3 months
 - b. Patients who are on steroid drops will be placed in a 14 day wash-out period, in both eyes, before they can be eligible. If in the discretion of the principle investigator, discontinuation of the topical treatment could pose any harm to the patient's ocular health, the patient will be excluded.
 - c. Patients who are on anti-histamines, oral (doxycycline or azithromycin) or topical antibiotics (bacitracin or erythromycin ointment) are eligible for as long as the doses have been stable in the past 2 weeks

- d. Patients who are on oral steroids or other anti-inflammatory or immunomodulatory medications are eligible for as long as the doses have been stable in the past 3 months
- e. Patients using glaucoma drops in either eye will be excluded (with the exception of rescue medication)

iii. Current systemic medications (see above)

iv. History of eye diseases and previous eye or eyelid surgery

- a. Patients who had eye surgery in the past 3 months prior to study are ineligible
- b. Patients who had penetrating corneal transplantation are not eligible

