5.1.1 Study Procedures

Patients will be instructed not to instill any eye drops one hour prior to any study visit.

SCREENING VISIT/RUN IN (Day -14 to -7) – Either Examining or Treating physician will perform.

The following information will be collected:

- Informed Consent
- Inclusion/exclusion
- Demographics
- Medical history and concurrent illnesses
- Concomitant medications
- Log/Dispense Rescue medications
- Ocular Surface Disease Index Questionnaire (OSDI)
- Schirmer test without anesthesia
- OSS (Corneal and conjunctival)
- Intraocular Pressure (IOP)
- Slit Lamp Examination (SLE)
- Dilated Fundus Exam (DFE)
- Rescue Med Recording

BASELINE VISIT (Day 1)- Treating Physician (Unmasked)

If run-in Visit was NOT performed:

- Informed Consent
- Inclusion/Exclusion
- Demographics

- Medical History and concurrent illnesses
- Dilated Fundus Exam (DFE)

Needed for all Baseline Day 1:

- Concomitant medications
- Urine Pregnancy Test
- Log/Dispense Rescue Meds
- Insert Study Drug/Control
- Best Corrected Spectacle Visual Acuity (BSCVA)
- VAS
- Schirmer without anesthesia
- OSS
- IOP
- SLE
- AE recording

VISIT 2 (14+/-3 days) – Examining Physician (Masked)

- Concomitant medications
- Log/Dispense Rescue Meds
- OSS
- IOP
- SLE
- Rescue med recording
- AE recording

VISIT 3 (28+/-3 days) – Examining physician (Masked)

- Concomitant medications
- Log/Dispense Rescue Meds
- VAS
- OSS
- IOP
- SLE
- Rescue med recording
- AE recording

VISIT 4 (42+/-3 days) – Examining Physician

- Concomitant Medications
- Log/Dispense Rescue Meds
- Pregnancy Test
- BSCVA
- VAS

- Schirmer W/O anesthesia
- OSS
- IOP
- SLE
- Dilated Fundus Exam
- Rescue med recording
- AE recording

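### The corneal staining co-primary has no rule for a missing Day 28 grade, so patients without one drop out by default although Day 14 and early-termination grades are collected; the contrast is biased only if leaving relates to the difference between the eyes

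*Combined protocol and SAP*

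**What the plan says.** The synopsis (Endpoint(s), Primary Efficacy, item 1) gives the endpoint as "Corneal staining score measured using OSS scale on Day 28" and the analysis as "The difference between the average corneal staining in the treated arm versus the average corneal staining in the sham arm will be compared statistically". Section 1.2.1 agrees on timing ("There will be two primary efficacy measures performed at day 28") and sizes the endpoint on "a clinically significant 3 point difference in the mean corneal staining between the treated arm versus the sham arm at day 28". Section 6.3 words the primary objective more loosely, as efficacy up to and including Day 28, but brings no earlier visit into an analysis.

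Staining is graded more often than that. In Table 1 (Section 5.1) the row "OSS (corneal and conjunctival" is marked at run-in, Day 1, Day 14, Day 28, Day 42 and early termination. Section 5.1.1 lists OSS again under "VISIT 2 (14+/-3 days". No stated analysis uses the Day 14 or early-termination corneal grades.

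The plan names no analysis set, missing-data rule, repeated-measures model, sensitivity analysis or dropout allowance. The title of Section 4 mentions withdrawal and replacement, but no text on either follows.

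**The concern.** An average of Day 28 grades can include only patients who have one. With no other rule, a patient who leaves between Day 14 and Day 28 is lost to the comparison, even though a post-baseline between-eye difference is on file.

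Two things are at stake. If leavers differ from stayers in their between-eye difference, the Day 28 contrast is shifted. It understates the benefit if patients with relatively bad sham eyes leave, and overstates it if patients with relatively bad treated eyes leave. Separately, the handling of missing grades on a co-primary endpoint stays open until someone decides it, possibly after the data have been seen.

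**Working it through.** **The plan's own figure.** Section 1.2.1 says: "With a power of 80% and significance level of 0.05, 23 persons in each group (having both eyes eligible) need to be enrolled". No SD is given, so the 23 cannot be reproduced. Inverting the two-sided two-sample formula gives SD = 3 × √(23/2) / (1.960 + 0.842) = 3.63, more than the largest SD possible on a 0–6 score (3.0). The paired form gives an SD of the difference of 3 × √23 / 2.802 = 5.14, just under the ceiling of √(36 − 9) = 5.20 for a mean difference of 3. Neither is a usable SD here, so the inputs below are assumptions.

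**Assumed inputs.**
- SD of one eye's grade: 1.5.
- Correlation between eyes: r = 0.3 or 0.6.
- Day 14 to Day 28 correlation: 0.6.
- True treated-minus-sham effect: 0 or −1.0 grade, with 70% of the effect present by Day 14.
- Leaving before Day 28: 10% or 20%, that is about 76 or 68 of 85 patients remaining.

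The SD of the between-eye difference is 1.5 × √(2(1 − r)): 1.775 at r = 0.3 and 1.342 at r = 0.6.

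**Formula.** Let k be the number of SDs by which the stayers' mean on whatever drives leaving falls below the whole cohort's mean. The bias of the Day 28 observed-case contrast is then k × c, where c is the covariance of the Day 28 difference with the driver (sham minus treated, so that positive means benefit understated), divided by the driver's SD:
- driver is the Day 14 between-eye difference: c = 0.6 × SD of difference = 1.065 or 0.805
- driver is the Day 14 sham grade: c = 0.6 × 1.5 × (1 − r) = 0.63 or 0.36
- driver is the average of both eyes at Day 14: c = 0, because with equal variances a difference is uncorrelated with a sum
- driver is the unseen Day 28 sham grade: c = 1.5 × (1 − r) = 1.05 or 0.60

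A simulation of 1,000,000 patients per scenario gave 0.129 (10% leaving) and 0.240 (20%) for the first driver at r = 0.3. Hence k = 0.129 / 1.065 = 0.121 and 0.240 / 1.065 = 0.225. In these scenarios leavers therefore sit 0.121 × 0.9/0.1 = 1.09 SD, or 0.225 × 0.8/0.2 = 0.90 SD, above the cohort mean on the driver, which is a strong dependence.

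**Results** (bias in grades, r = 0.3 / r = 0.6):

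| What drives leaving | Formula, 10% | Simulated, 10% | Formula, 20% | Simulated, 20% | Simulated range left after using Day 14 |
|---|---|---|---|---|---|
| Day 14 between-eye difference | 0.129 / 0.097 | 0.129 / 0.098 | 0.240 / 0.181 | 0.240 / 0.182 | 0.00 |
| Day 14 sham eye | 0.076 / 0.044 | 0.076 / 0.044 | 0.142 / 0.081 | 0.144 / 0.082 | 0.00 |
| Day 14 worse eye (true effect −1.0) | – | 0.032 / 0.022 | – | 0.059 / 0.037 | 0.00 |
| Average of both eyes, Day 14 | 0 | 0.00 | 0 | 0.00 | 0.00 |
| Unseen Day 28 sham eye | 0.127 / 0.073 | 0.128 / 0.073 | 0.236 / 0.135 | 0.238 / 0.135 | 0.05 to 0.16 |

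The first cells at r = 0.3 were used to set k; the other formula values are predictions, and they match. By the same formula, leaving driven by a bad treated eye gives the same sizes with the opposite sign.

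**Second set of assumptions.** With 85 pairs, SD of the difference 1.5, Day 14 to Day 28 correlation 0.5 to 0.7, 10% to 15% leaving, and odds of leaving rising by a factor e per SD of the Day 14 difference, the observed-case contrast understated a 1-grade effect by 0.07 to 0.14. With e² per SD it understated it by 0.11 to 0.21. The standard error was 0.17 to 0.18 with or without Day 14.

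**Carrying the last grade forward** is no substitute: with a true effect of −1.0 it left −0.07 to +0.14.

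**The case against.** Several points against this stand, and they limit the claim.

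- *Exclusion is not written down.* A reader might infer that the plan excludes patients without a Day 28 grade. It does not say so. The defect is the absence of a rule, and exclusion is only what follows by default.
- *Informative leaving is not documented.* A reader might infer that a worsening sham eye or a pressure rise in the treated eye leads patients to stop. The synopsis and Section 5.2 answer both with rescue medication, and Table 1 records rescue at the later visits. Treatment is a single resorbable insert (Section 1.2), so there is no continuing dosing to stop. Leaving for such reasons is possible, but the documents do not establish it.
- *Outcome-related leaving is not enough.* A reader might infer that any leaving tied to how the eyes are doing biases the result. Both eyes leave together, and leaving tied to their shared level gave 0.00.
- *The model's near-zero bias is by construction* wherever leaving was generated from Day 14 grades. It does not hold when unseen grades drive leaving.
- *The size is modest.* The largest figure, 0.24, is 24% of an assumed 1-grade effect but 0.24/3 = 8% of the planned 3-point difference. In the second set, the bias of 0.07 to 0.14 is below one standard error. Staining power is not at issue: at the SD implied by 23 per group it stays above 99% with 68 pairs.

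What survives is that the plan collects grades that bear on missing Day 28 values, gives them no use, and states no rule. Remedying that costs no new data.

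**Conclusion.** The point holds in a limited form. The Day 28 staining comparison has no analysis set or missing-data rule, and by default loses patients whose Day 14 or early-termination grades exist. Bias arises only if leaving relates to the between-eye difference. Its illustrative size is about 0 to 0.24 grade with 10% to 20% leaving, resting wholly on assumed SD, correlations, dropout and strength of dependence. The direction depends on which eye drives leaving, which the documents do not say. Using Day 14 removes the part predicted by observed grades; it does not remove the part driven by unseen ones. This is a worthwhile, inexpensive improvement and not a fatal flaw.

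**What to change.** In the synopsis and Section 1.2.1:

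1. Define the staining co-primary as the Day 28 treated-minus-sham contrast from a repeated-measures model on each patient's between-eye difference at Day 14 and Day 28, adjusted for the baseline between-eye difference.
2. Define the analysis set as every randomised patient with any post-baseline OSS, and report how many have none.
3. Use an early-termination grade as a Day 14 or Day 28 value only if it falls within that visit's ±3-day window (Days 11–17 or 25–31) and no scheduled grade exists. Otherwise model it at its actual day, with the time trend and correlation specified in advance. Assigning it simply to the nearest visit would not do: a Day 16 grade could duplicate an existing Day 14 grade, and a Day 22–24 grade would count as Day 28 outside the window.
4. Keep the observed-case Day 28 comparison as a sensitivity analysis, and add a missing-not-at-random one, for example delta-adjusted.

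The cost is wording, a missing-at-random assumption and a slightly more complex model; no visit or measurement is added. The change applies to staining only: VAS is not collected at Day 14, so the symptom co-primary needs its own missing-data rule. It also leaves open how rescue use before Day 28 is handled, which should be stated separately.

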“patient” related factors in this small scale study (such as difference in use of computers or sleep/wake hours, environmental factors such as humidity during this short-term study, or severity of ocular surface inflammation particularly whether underlying Sjögren’s syndrome is present or not, as well as the severity of evaporative component of the dry eye) will be comparable between the treatment and the control.

4- Also, this design allows both eyes of the same patients enrolled as study eyes thereby decreasing the sample size, hence the cost.

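### Treated and sham eyes are paired within each patient, but no section says whether the co-primary analyses use the pairing or the Day 1 values, or whether the outcome is a Day 28 score or a change

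*Combined protocol and SAP*

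**What the plan says.** The design is fully paired. The synopsis gives the sample size as "85 patients [1 treatment eye/1 control eye = 170 eyes] will be enrolled at a single site". Under Dose/Route/Schedule the right eye is randomised and "The left eye will automatically receive the alternative". Section 1.2 (points 3 and 4) presents this as a strength: patient-level factors are comparable between treatment and control, and "this design allows both eyes of the same patients enrolled as study eyes thereby decreasing the sample size".

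The analysis is described much more briefly. For corneal staining, the synopsis (Primary Efficacy) says "The difference between the average corneal staining in the treated arm versus the average corneal staining in the sham arm will be compared statistically". The symptom endpoint has parallel wording: "the average most bothersome symptom in the treated arm versus the average most bothersome symptom in the sham arm will be compared statistically". Section 1.2.1 uses two-group language for the size of the trial: "85 persons in each group (having both eyes eligible) need to be enrolled". The protocol has no statistical analysis section, and no section names a test, a within-patient difference or a baseline term.

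The form of the outcome also varies. The synopsis sets the staining endpoint as a Day 28 score, and the power statement in 1.2.1 refers to a "3 point difference in the mean corneal staining between the treated arm versus the sham arm at day 28". The lead-in to the same section calls the measures "The improvement in corneal staining score (using the OSS scale) and improvement in the most bothersome symptom", and sections 2.1 and 6.3 also speak of improvement. Improvement is not defined there as change from Day 1.

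The data for a paired, baseline-adjusted analysis are already planned. Section 4.1.1 (item 8) requires Day 1 staining and symptom scores in both eyes, Table 1 and section 5.1.1 schedule both measures at Day 1 and Day 28, and section 5.1 has every test done in both eyes.

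**The concern.** With two eyes per patient, the standard error of the treatment difference depends on the between-eye correlation. A comparison of two arm averages, sized as two groups of persons, can be carried out with or without that correlation, and the text does not say which. It also leaves open whether the Day 28 score, the change from Day 1 or a baseline-adjusted difference is analysed. These choices give different intervals and p-values from the same data. An interim analysis is planned at 6 months, so the choice could be made after some data have been seen.

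The stake is precision and pre-specification. With complete pairs the difference in means is the same whether or not the pairing is used. Because eyes are randomised within patient, Day 28 score and change from Day 1 have the same expected treatment difference.

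**Working it through.** **The plan's own figures.** Section 1.2.1 gives 23 and 85 per group (80% power, 0.05) for 3 and 30 points, citing a published source for the SDs without stating them. Two-sided and unpaired, SD = δ·√(n/2)/(1.960 + 0.842):
- staining: 3 × √11.5 / 2.802 = 3.63, but a 0–6 scale allows at most 3.0;
- symptom: 30 × √42.5 / 2.802 = 69.8, but a 0–100 scale allows at most 50.

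The paired form, SD of the difference = δ·√n/2.802, gives 5.14 and 98.7. With a mean difference of 30, the second cannot exceed √(100² − 30²) = 95.4. The first is just under its bound of √(6² − 3²) = 5.20 and would need a negative between-eye correlation. The stated sizes therefore do not reveal whether pairing was assumed. That they cannot be reproduced is a separate matter, and nothing below depends on it.

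**Assumptions.** 85 complete pairs, two-sided 5%. The documents give no SD or correlation, so I assume SD 28 for the symptom scale, SD 2 for staining, and between-eye correlation ρ of 0.3, 0.5 or 0.7.

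**Formulas.** Unpaired SE = SD·√(2/85). Paired SE = SD·√(2(1−ρ)/85). Their ratio is 1/√(1−ρ). Half-width = t × SE, with t = 1.974 (168 df) unpaired and 1.989 (84 df) paired. Unpaired type I error = 2·Φ(−1.974/√(1−ρ)). Unpaired power = Φ((δ − 1.974 × unpaired SE)/paired SE). Paired power comes from the noncentral t with 84 df.

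| | ρ = 0.3 | ρ = 0.5 | ρ = 0.7 |
|---|---|---|---|
| SE ratio, unpaired to paired | 1.20 | 1.41 | 1.83 |
| Type I error if unpaired | 1.8% | 0.5% | 0.03% |
| Symptom half-width, unpaired vs paired (mm) | 8.5 vs 7.1 | 8.5 vs 6.0 | 8.5 vs 4.7 |
| Symptom power at 10 points | 66% vs 79% | 69% vs 90% | 74% vs 99% |
| Staining half-width, unpaired vs paired | 0.61 vs 0.51 | 0.61 vs 0.43 | 0.61 vs 0.33 |
| Staining power at 0.5 points | 34.0% vs 48.6% | 31.3% vs 62.5% | 26.5% vs 83.7% |
| Staining power at 1 point | 94% vs 97% | 97% vs >99% | 99% vs >99% |

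Worked line for the symptom at ρ = 0.5: unpaired SE = 28 × √(2/85) = 4.30; paired SE = 4.30 × √0.5 = 3.04; half-widths 1.974 × 4.30 = 8.5 and 1.989 × 3.04 = 6.0. At 30 symptom points or 3 staining points, power is about 100% either way, for staining even at SD 3. A simulation of 20,000 trials gave unpaired type I errors of 0.6% at ρ = 0.5 and 0.05% at ρ = 0.7, the same order as the formula.

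**Baseline values.** Let r be the correlation between the Day 1 and Day 28 between-eye differences, with equal variances. Relative to the Day 28 difference alone, the variance is 2 − 2r for change and 1 − r² for baseline adjustment: 1.40 and 0.91 at r = 0.3, 1.00 and 0.75 at 0.5, 0.60 and 0.51 at 0.7. Change is noisier than the Day 28 score when r is below 0.5; adjustment is not worse than either, apart from the small cost of estimating one slope. The SE falls by 1 − √(1 − r²), which is 2%, 6% and 13% at r = 0.2, 0.35 and 0.5.

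**Responders.** Assume 30% sham and 45% treated, with within-patient correlation 0.2, 0.3 or 0.5. At 0.3, both eyes respond with probability 0.30 × 0.45 + 0.3 × √(0.30 × 0.70 × 0.45 × 0.55) = 0.203, leaving discordant probabilities of 0.097 and 0.247. In 200,000 simulated trials per setting:
- unpaired chi-square: power about 53% at each correlation;
- asymptotic McNemar: 62%, 68%, 83%;
- mid-p McNemar: 60%, 66%, 81%;
- exact McNemar: 54%, 60%, 76%.

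With 30% in both arms and correlation 0.3, type I error was about 2% unpaired, 5.3% asymptotic and 4.5% mid-p.

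**The case against.** The strongest reply is that the documents are silent rather than wrong. Section 1.2 names within-patient comparability as a strength, so a paired analysis is at least as natural a reading as an unpaired one. This stands: a reader might infer from the two-group wording that an unpaired test is prescribed, but no test is named.

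A reader might also infer that the saving claimed in section 1.2 is lost without a paired test. It is not. Enrolling both eyes supplies 85 eyes per arm from 85 patients, where one eye per patient would need 170, and this holds under any test. Only the further gain in precision depends on pairing.

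The consequence is also small where the trial was sized. Even at 15 symptom points, half the planned effect, unpaired power is 97% to 99.7% under these assumptions, against 98% to 100% paired. At one staining grade it is 94% to 99%. The larger losses occur at effects chosen here and at assumed SDs and correlations. This stands and limits the weight of the point. Interval width, however, is affected whatever the true effect.

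A plain paired t-test would recover all of the pairing gain, with baseline adjustment adding only 2% to 13%. That is fair, but adjustment is free and settles the choice between score and change. Finally, the exact McNemar test gains almost nothing at correlation 0.2 (54% against about 53%), so the version has to be named.

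**Conclusion.** The point holds as a gap in specification with a cost in precision. The plan does not state whether the co-primary analyses use the pairing or the Day 1 values, and it describes the outcome in two forms. Ignoring the pairing would inflate the standard error by 20%, 41% or 83% at assumed between-eye correlations of 0.3, 0.5 or 0.7. These figures rest on 85 complete pairs and positive correlation; the half-widths and powers also rest on the assumed SDs.

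Two stronger readings are not supported. One is that the treatment estimate is biased: the difference in means is the same over complete pairs, and score and change have the same expected difference under within-patient randomisation. The other is that false positives increase: with positive correlation an unpaired test is conservative. Nor is the trial underpowered on this account at its planned effects. The change is worth making because it is free and narrows the reported intervals.

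**What to change.** In the synopsis and sections 1.2.1, 2.1 and 6.3, state one primary analysis for each co-primary: a regression of the within-patient (treated minus sham) Day 28 difference on the within-patient (treated minus sham) Day 1 difference. The intercept, with the Day 1 difference left uncentred, is the treatment effect and is reported with its 95% confidence interval.

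If a mixed model is preferred, enter each eye's deviation from the patient's mean baseline and that mean as separate terms. A patient random effect with only eye-level baseline is not equivalent. Compare responders with the mid-p McNemar test.

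One point must be settled first for the symptom. The synopsis sets the most bothersome symptom separately for each eye, whereas sections 4.1.1 and 5.1 can be read as one symptom per patient. If the two eyes are scored on different symptoms, the treated-minus-sham difference is hard to interpret, so these passages must be reconciled.

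The cost is wording only. Both measures are already collected in both eyes on Day 1 and Day 28, so no patients, visits or measurements are added.
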